Motivational Interviewing (MI). Typically offered as a brief intervention of 1-2 sessions, Motivational Interviewing (MI, Miller & Rollnick, 2012) has a strong record of efficacy in the prevention and treatment of alcohol and other drug use disorders (Copeland et al., 2015; Miller & Rollnick, 2012). MI assumes that the responsibility and capability for change lie within the client and needs to be evoked (rather than created or installed). Baer, Peterson and Wells (2004) provide some rationale for utilizing brief feedback and motivational intervention with street living youth - the intervention is less costly and demands much less of a hard-to-reach population than more intensive interventions. Utilizing a sample of runaway adolescents recruited from a runaway shelter, Slesnick et al. (2013) found that substance use reductions were significant for those assigned to MI even to two years post-treatment. The advocate will administer MI. Four principles guide the practice of MI: express accurate empathy, develop discrepancy, roll with resistance and support self-efficacy. The Project Match manual was adapted for homeless/runaway youth in prior trials in consultation with [name] and [name] (NIAAA grant no. R01AA12173 and NIDA grant R29DA11590). Adaptation of the manual included attention to the unique life situation of homeless youth in understanding motivations and challenges to recovery while homeless. Session 1 begins with a period of open-ended MI, to establish therapeutic rapport and elicit client change talk. In session 2 the advocate continues to focus on enhancing intrinsic motivation for change, developing discrepancy, transitioning as appropriate into the negotiation of a change plan and evoking commitment to the plan.

Housing + Opioid and Related Risk Prevention Services. Those randomized to receive housing + opioid and related risk prevention services will receive all the above and also receive 6-months of rental and utility supports in an apartment of their choosing.

All youth completed a **baseline and follow-up assessment** which included self-report, interview, and physiological measures, with the following outcomes.

Primary Outcomes: **1)** time to OUD (SCID) (UH3) **2)** % days opioid use (Form 90) (UG3, UH3).

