Secondary Outcomes: **1)** % days other alcohol/drug use (Form 90), **2)** drug use consequences (SIP) **3)** HIV risk score (0-7) **4)** % days housed (Form 90), **5)** BDI-II depression score, **6)** Physical health score (SF-6), **7)** % days employed and % days in school/training (Form 90), **8)** resilience score (BRS), **9)** coping (task, emotion and avoidance) scores (CISS) **10)** cognitive distortions score (CD-QUEST), and **11)** self-regulation score (SSRS).

Mediators: Primary: **1)** # of service contacts (service log), **2)** working alliance score (WAI), **3)** social support (SNI): number and satisfaction of support persons, and **4)** # of violence/victimization exposures (HEQ).

Secondary: **1)** Stress (2 dv's) self-reported stress score (Cohen's PSS), and physiological hair cortisol level, and **2)** Self-efficacy (3 dv's): HIV, substance use, and perceived personal control scores.

Study Aims were as follows:

Specific Aim 1. Evaluate the relative efficacy of housing + opioid and related risk prevention services compared to prevention services alone (N = 240). Hypothesis. Youth receiving the 6-month housing + prevention services will show better 3, 6, 9 and 12 month outcomes than those receiving prevention services alone. Fewer Housing First youth will progress to OUD and will be more likely to remain housed at one year.

Specific Aim 2. Test the effects of the primary and secondary mediators on the primary outcome (opioid use/time to OUD) and secondary outcomes. Hypothesis. Inasmuch as the intervention triggers

successful social micro and meso-system interactions or social resources (e.g., advocate and social service meetings), individual resources will be activated – e.g., stress will decrease and self-efficacy will increase, leading to multiple positive outcomes.

Specific Aim 3. Explore how moderators affect individual's response to housing + opioid and related risk prevention services.

Statistical Analysis Plan

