Study Aim 2. To test the proposed behavioral change mechanisms (i.e., social and individual resources), a series of path analysis will be conducted. Specifically, we will first test whether the primary mediator (e.g., service connections, social support) or secondary mediator (e.g., self-efficacy, stress) assessed at the 3- or 6-month follow-up mediates the association between intervention and outcome at 6-month and 9/12-month follow-up, respectively. We expect that the intervention condition with the housing component will produce greater improvement in social/individual resources, which in turn will predict better outcomes. We will also estimate serial mediation models, in which both primary and secondary mediators are included (Figure 1), to test whether intervention first affects social resources, which then lead to changes in individual resources and subsequent outcomes. In these models, the baseline assessment of the mediators and outcomes will be controlled for in the analysis. Following MacKinnon and colleagues (MacKinnon et al., 2007), the product of the coefficient of the path from the independent variable to the mediator(s) and the coefficient of the path from the mediator(s) to the outcomes will be computed as the indirect (mediation) effect between the intervention and outcomes. The strength and significance of the mediation will be estimated using a bootstrap sampling method (Shrout & Bolger, 2002).

Study Aim 3. The effect of the moderating variables (age, sex, race/ethnicity, sexual orientation, childhood abuse history, and baseline substance use and service connection) will be tested by examining the interaction between intervention type and each moderator in predicting outcome slopes in the growth models and survival analysis. The contrast between intervention conditions will be multiplied by each moderator variable to form an interaction term. Next, the interaction terms will be included in the analyses for Aim 1 for the primary/secondary outcomes, one at a time, and their strength of association with the outcome slope will be assessed while controlling the direct effects of the predictors on outcome and the direct effect of moderator variables on outcome. If the interaction term is significant, this suggests moderation.

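### Aim 2 adjusts its mediation models only for baseline mediators and outcomes, leaving the mediator-to-outcome path open to avoidable confounding by baseline variables the trial already collects, most clearly for time to OUD

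*Combined protocol and SAP*

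**What the plan says.** Under Study Aim 2 in the SAP, each mediator is "assessed at the 3- or 6-month follow-up mediates the association between intervention and outcome at 6-month and 9/12-month follow-up, respectively". The product of the arm-to-mediator and mediator-to-outcome coefficients "will be computed as the indirect (mediation) effect between the intervention and outcomes", and the inference is stated as: "The strength and significance of the mediation will be estimated using a bootstrap sampling method". The only covariate rule for these models, single or serial, is: "In these models, the baseline assessment of the mediators and outcomes will be controlled for in the analysis".

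Under Study Aim 3 the SAP lists further baseline variables: "age, sex, race/ethnicity, sexual orientation, childhood abuse history, and baseline substance use and service connection". They are used as moderators, and "the interaction terms will be included in the analyses for Aim 1 for the primary/secondary outcomes, one at a time". The plan does not carry them into the Aim 2 models, and it describes no sensitivity analysis for mediator-outcome confounding.

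Two other places matter. Specific Aim 2 in the protocol includes time to OUD among the outcomes to be explained. Sample Inclusion Criteria, item 3, admits only youth without OUD.

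**The concern.** Arm is randomised; the mediator is not. A youth's level of victimisation, support, stress or self-efficacy at 3 or 6 months may share causes with that youth's later opioid use, depression or HIV risk. Childhood abuse history is an obvious candidate, and so is baseline drug use when the outcome is something else. Controlling the baseline mediator and outcome removes confounding that runs only through those two readings. It does not remove a cause that also acts on both variables after baseline. The bootstrap deals with sampling error, not with this bias.

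Aim 2 is worded as a causal mechanism: social resources activate individual resources, which improve outcomes. If housing really shifts a mediator, residual confounding of the second path can appear as a significant indirect effect that is only a marker of the shared cause. If the two effects of the shared cause have opposite signs, it can instead hide real mediation.

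**Working it through.** **The plan's own figures.** The Statistical Power Analysis gives power of .93 (one mediator) and .82 (serial). Neither can be reproduced, because the Aim 2 path values and alpha are not stated. Taking power(a) × power(b), two-sided .05 and b = .30, power of .93 needs a standardised a path of about .22 at N = 240 or .24 at N = 204 (d about .45 to .49). That is plausible but unverified. Power says nothing about bias, so the check below is separate.

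**Inputs from the documents.** N = 240; 15% attrition leaves 240 × .85 = 204; allocation 1:1.

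**Assumed, because the documents give nothing.** True mediator effect zero. One binary shared cause C, coded ±1, with a correlation of .3 with baseline mediator M0 and with baseline outcome Y0. Carry-over .5, residual SD .8, arm effect on the mediator d = .30 to .49. The models are M1 = .5·M0 + d·T + c·C + error and Y1 = .5·Y0 + c·C + error. The remaining direct effect c takes the values .1, .15, .2 and .3. With ±1 coding, the gap between groups is 2c, so c = .3 is a .6 SD gap.

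1. *What the planned adjustment leaves.* The correlation of M0 with Y0 is .3 × .3 = .09. Together they explain 2 × .3² / 1.09 = .165 of C, leaving v = .835.
2. *Spurious mediator coefficient.* b* = c²v / (c²v + .64). At c = .3: .0751 / .7151 = .105.
3. *Chance that the b path is significant.* z = b*√N / √(1 − b*²) and P = Φ(z − 1.96) + Φ(−z − 1.96). At c = .3: z = 1.51 and P = .33 (N = 204); z = 1.64 and P = .37 (N = 240).
4. *Chance that the a path is significant.* SE = 2√(.64 + .91c²) / √N. At c = .3, N = 204, d = .30: SE = .119, z = 2.52, P = .71. At N = 240, d = .49: SE = .110, z = 4.47, P = .99.
5. *False mediation* (both paths significant) is the product. At c = .3 it runs from .71 × .33 = .23 to .99 × .37 = .37.

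| c | b* | False mediation, formula | False mediation, simulation |
|---|---|---|---|
| .1 | .013 | .04–.05 | .04–.05 |
| .15 | .029 | .05–.07 | .05–.07 |
| .2 | .050 | .08–.12 | .08–.12 |
| .3 | .105 | .23–.37 | .23–.34 |

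Repeat simulations at c = .3 reach .38 at the upper end. With C in both equations, b* is zero and the rate is .05 × P(a path), so at most .05.

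**A real effect is inflated too.** With a true b of .30, the planned adjustment estimates about .31, .35 and .40 at c = .1, .2 and .3. Adding C returns .30.

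**No informative baseline outcome** (a linear stand-in for time to OUD). Only M0 now absorbs C, so v = 1 − .3² = .91. At c = .2, b* = .0364 / .6764 = .054 and the b path is significant with chance .12 (N = 204) or .13 (N = 240), against .11 and .12 above. At c = .3, b* = .0819 / .7219 = .113 and the chance is .37 or .42, against .33 and .37.

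**The case against.** The strongest defence is that the plan already does much of the work. It measures the mediator before the outcome and controls both baselines. For % days opioid use and % days other alcohol/drug use, the baseline outcome is baseline use of the same substance. A reader might infer that baseline substance use is missing from Aim 2 altogether. It is not. Baseline service connection is likewise controlled where it is the mediator, if a baseline value exists.

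The alarming rates also need a strong confounder. The association of C with follow-up is about .5 × .30 + c. A historical cause whose link stays at .30 implies c = .15, where false mediation is close to nominal. At c = .2 and .3 the link rises to .35 and .45 within the follow-up year, and nothing in the documents supports that. This stands as a limit on the claimed size. It does not close the gap, since several causes can add up. Four independent causes of .1 SD in the same direction act like one of √4 × .1 = .2 SD, if their combined correlation with each baseline is still .3.

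It is also fair that the documents do not argue for each of the seven variables as a shared cause of each mediator-outcome pair. But nothing in the documents shows abuse history entering the Aim 2 models, and no harm from adding it is apparent beyond some degrees of freedom.

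**Conclusion.** The point holds as a gap in prespecification. Aim 2 leaves a non-randomised path open to confounding that variables already in hand could reduce: childhood abuse history throughout, and baseline substance use wherever it is not the baseline outcome. Time to OUD is the clearest case, because its baseline value is the same for everyone.

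The size is unknown. Under the assumed linear model with one shared cause, false mediation ranges from nominal (.04 to .05 at .1 SD) to about .23 to .34 at .3 SD, and is higher where no informative baseline outcome exists.

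A reader might infer that the Aim 2 results are bound to be confounded, or that the main trial result is in doubt. The documents support neither. They give no confounder strengths, and the weaker settings show little or no harm. The randomised Aim 1 comparison does not use these models and is not affected by this omission. The change is worth making, but it concerns the mechanism claims only.

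**What to change.** In Study Aim 2, replace the covariate sentence with:

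*All mediator and outcome equations, single and serial, will include the baseline mediator and baseline outcome (where these exist and vary), together with childhood abuse history, baseline substance use, baseline service connection, age, sex, sexual orientation and race/ethnicity (each entered once where it coincides with the baseline mediator or outcome).*

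Add that indirect effects will be reported with the caveat that unmeasured mediator-outcome confounding may remain; a sensitivity analysis for it would be a useful addition. The caveat is needed even after the change. For example, the SBOA section links longer homelessness to both substance use and victimisation, and duration of homelessness is not on the Aim 3 list.

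The cost is SAP wording and a few degrees of freedom out of 204 to 240 youth. Aim 3 already requires the variables. Naming them in advance also prevents covariates being chosen after the results are seen.

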“Prevention of OUD: The HOME (Housing, Opportunities, Motivation and Engagement) Randomized Trial”

NCT04135703

6/28/2024

Study Protocol

Overview of Design

240 homeless youths between the ages of 18 to 24 years recruited from the streets and drop-in center/shelters will be randomly assigned to 1) 6-months of housing + opioid and related risk prevention services (n = 120), or to 2) opioid and related risk prevention services alone (n = 120). Using an intent to treat design, follow-up assessments will be completed at 3, 6, 9 and 12 months post-baseline. Upon completion of the baseline assessment interview, youths will be randomly assigned to the intervention conditions using a computerized urn randomization program. Four advocates will provide services so that advocate effects can be examined (Baldwin et al., 2011), and each advocate will provide all opioid and related risk prevention services to the youth on their caseload. Advocates will be crossed by condition to “equate” conditions on advocate characteristics.

Sample Inclusion Criteria.

1. Youth were between the ages of 18 to 24 years. Our experience is that landlords will not accept leases signed by youth ages 16-17 years. “Homeless youth” commonly refers to those up to the age of 24 years (Robertson & Toro, 1999; USICH, 2010), thus, this age range generally reflects the age range of the homeless youth population served by providers across the country.
2. Youth met the criteria for homelessness as defined by the federal McKinney-Vento Act (2002) as “lacking a fixed, regular, stable, and adequate nighttime residence” and includes “living in a publicly or privately operated shelter designed to provide temporary living accommodations, or a public or private place not designed for, or ordinarily used as, regular sleeping accommodations for human beings.”
3. Youth failed to meet DSM 5 criteria for Opioid Use Disorder as assessed by the SCID (First et al., 2015).

Screening and intake. Project staff maintain offices within the drop-in center. An RA engaged and screened youth to determine basic eligibility for the study. After the brief screening and stated interest in the project, written consent was obtained and the Structured Clinical Interview for DSM-5 Disorders (SCID) (First, Williams, Karg, & Spitzer, 2015) section on Opioid Use Disorder, was administered to determine formal eligibility.

Project Intervention: Opioid and Related Risk Prevention Services

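### Aim 2 promises control for baseline mediators, but working alliance has no baseline value, and the plan names no substitute covariate for its non-randomised path to the outcome

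*Combined protocol and SAP*

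**What the plan says.** The Study Aim 2 paragraph of the Statistical Analysis Plan tests whether mediators measured at 3 or 6 months carry the intervention effect to outcomes at 6 and at 9/12 months, singly and in serial models. It adds that in these models "the baseline assessment of the mediators and outcomes will be controlled for in the analysis". No mediator is exempted.

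The protocol's mediator list gives four primary mediators:
- "of service contacts (service log")
- "working alliance score (WAI")
- "social support (SNI): number and satisfaction of support persons"
- "of violence/victimization exposures (HEQ")

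On timing, the Overview of Design says: "Upon completion of the baseline assessment interview, youths will be randomly assigned to the intervention conditions". Each advocate then serves the youth on an assigned caseload. Screening and intake are done by a research assistant.

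The third inclusion criterion admits only youth who do not meet criteria for OUD. Specific Aim 2 names opioid use and time to OUD as the primary outcomes to be tested for mediation.

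**The concern.** Randomisation protects the path from intervention to mediator. It does not protect the path from mediator to outcome, where youth with high and low alliance may differ in ways that also drive the outcome. The plan's stated defence on that path is adjustment for the baseline mediator and the baseline outcome.

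For WAI the first of these does not exist. Youth who were already better connected to services may form stronger alliances and also do better for other reasons. The product of the two paths would then credit the alliance with some of that difference. The WAI result would be reported beside those for social support and victimisation as if all had been adjusted alike.

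**Working it through.** **1. Can each primary mediator have a baseline value?**

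| Mediator | Baseline value | Basis |
|---|---|---|
| Service contacts (log) | Possible, not specified | The scope of the log is not defined. Aim 3 lists baseline service connection as a moderator. Aim 2 uses nearly the same term for the mediator. The Aim 1 text counts contacts with other providers apart from intervention sessions. |
| Working alliance (WAI) | No | Baseline precedes assignment and advocate services. |
| Social support (SNI) | Yes | Can be asked of any youth at interview. |
| Victimisation (HEQ) | Yes | Same. |

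So one of four certainly has no baseline value, and for one more the matching covariate is unstated. This takes the WAI to rate the alliance with the project advocate; the documents do not say so outright, but name no other provider of the intervention.

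**2. What control remains on the WAI-to-outcome path?**

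- Continuous outcomes, such as % days opioid use: the baseline outcome is still controlled.
- Time to OUD: nobody has OUD at entry, so the baseline outcome is constant and adjusts for nothing. Neither part of the plan's sentence supplies control here.

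**3. How large could the bias be?** The plan has no figure to reproduce on this point. Its mediation powers (.93 and .82) come without Aim 2 coefficients and do not bear on it. The following is an illustration in a linear model, with every parameter assumed.

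Let U be a stable baseline trait. It loads g on WAI and .3 directly on the outcome. The baseline outcome Y0 loads .5 on U, and Y0 loads .4 on the later outcome. The true WAI-to-outcome path is zero.

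- No covariates: spurious path = g × (.3 + .4 × .5) = .5g.
- Y0 controlled: spurious path = .3 × g × (1 − .5²) / (1 − (.5g)²) = .225g / (1 − .25g²).
- Y0 and U controlled: 0.

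| g | No covariates | Y0 controlled | Y0 and U controlled |
|---|---|---|---|
| .2 | .10 | .045/.99 = .05 | 0 |
| .3 | .15 | .0675/.9775 = .07 | 0 |
| .5 | .25 | .1125/.9375 = .12 | 0 |

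A least-squares run on 1,000,000 simulated records gave .101, .152 and .250 with no covariates, .046, .070 and .121 with Y0, and .001 each time with both. With a true path of .30 the same run gave .40 to .55, .35 to .42 and .30.

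**4. What does this do to the indirect-effect test?** Take 240 × .85 = 204 youth, so the standard error is about 1/√204 = .070. With Y0 controlled, the spurious path divided by its standard error is .65, .99 and 1.71. A two-sided 5% test of that path alone then rejects in about 10%, 17% and 40% of trials.

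The plan tests the product of two paths, so the intervention-to-mediator path must also be detected. With an assumed standardised path of .15 and N = 204, its power is about .57. A joint-significance approximation gives .57 × (10%, 17%, 40%) = about 6%, 10% and 23%, against .57 × 5% = about 3% without confounding. A larger first path raises all of these.

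**The case against.** The strongest reply is that any reader will take the sentence to mean that baseline is controlled where it was measured, that this concerns one mediator in a mechanism aim, and that no Aim 1 estimate changes. The last two points stand. The first does not settle the matter, because the plan still names nothing in place of the missing covariate.

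Several stronger readings are tempting but not supported:

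- *Two of the four primary mediators cannot exist at baseline.* This holds for service contacts only if the log covers project contacts alone, which the plan does not say. A baseline service connection variable is planned for Aim 3. The gap is one of specification.
- *The affected mediators have no protection at all.* The baseline outcome is still controlled for continuous outcomes, the intervention-to-mediator path is randomised, and the mediator is measured before the outcome. In the illustration the baseline outcome removes about half of the bias. The statement comes close to true only for time to OUD.
- *False mediation would be common, at the rate at which a confounded mediator-to-outcome path is significant with no covariates.* That ignores the baseline outcome and tests only one of the two paths in the product.
- *FIML would invent an alliance for youth who never met an advocate.* FIML maximises the likelihood of the observed data and does not fill in scores. The Missing Data section also has missingness patterns examined first and allows pattern mixture models. The fair criticism is that the plan has no rule for a youth whose alliance is undefined, as opposed to unobserved.
- *The WAI model should be limited to youth who met their advocate.* Such a meeting happens after randomisation and may differ by arm. Restricting to it would remove randomisation from the one path that has it.

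**Conclusion.** The point holds for WAI. The stated adjustment cannot be carried out for that mediator, and no replacement is named. For time to OUD, the sentence leaves the WAI-to-outcome path with no effective control. For service contacts, the plan should say whether baseline service connection is the covariate.

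The direction of bias, towards mediation, assumes a trait that raises alliance and also improves outcome. Its size depends on correlations the documents do not give. With the loadings assumed above, the spurious path is about .05 to .12 for continuous outcomes; .10 to .25 is the corresponding linear figure where the baseline outcome is no help. The second range is only a guide for time to OUD, which is modelled on the hazard-odds scale. Aim 1 is unaffected.

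**What to change.** Amend the Study Aim 2 text as follows:

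1. State that WAI has no baseline value.
2. In the WAI models, adjust the mediator-to-outcome path for baseline service connection, baseline social support (SNI) and the baseline outcome. When the outcome is time to OUD, use baseline % days opioid use in place of the constant OUD status.
3. Name baseline service connection as the baseline covariate for service contacts.
4. Describe the WAI-to-outcome path as non-randomised wherever it is reported.
5. Report the proportion with no advocate contact by arm, and do not treat their WAI as ordinary missing-at-random data.
6. Allow an analysis of engaged youth only as a sensitivity analysis, with the caution that it conditions on a post-randomisation event.

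The cost is SAP wording, a few extra covariates from variables the plan already names at baseline, and a more cautious label on the WAI result. The adjustment removes bias only so far as these covariates capture the confounding trait; the zero in the illustration assumes that they do so fully.
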